## 6. Tolerability of ivabradine and events of interest

### a) Symptomatic bradycardia

Use the EVENT data to get unique participant level status.

If EVENT.EVBRDC=1 and (non-missing EVENT.EVDT-PATIENT.DISDT  $\leq$  194) then symptomatic bradycardia=1; else if participant is assessed at any time point, symptomatic bradycardia=0.

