**5.4.3 Phone Call**

At 90 (+/-7) days post-discharge, participants should be contacted by the site (phone call) to assess for event status, current medication use and doses, and tolerability of ivabradine, specifically

- Symptomatic bradycardia
- Symptomatic hypotension
- Other symptoms leading to ivabradine discontinuation

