### b) Symptomatic hypotension

Use the EVENT data to get unique participant level status.

If EVENT.EVHYPO=1 and (non-missing EVENT.EVDT-PATIENT.DISDT  $\leq$  194) then symptomatic hypotension=1; else if participant is assessed at any time point, symptomatic hypotension=0.

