### c) Other symptoms leading to ivabradine discontinuation unique participant level status

Other symptoms leading to ivabradine discontinuation is obtained from the AE data.

If AE.AETYP=3 and (non-missing AE.AESTDT-PATIENT.DISDT  $\leq$  194) then other symptoms leading to ivabradine discontinuation=1;

Else if participant is assessed at any time point, other symptoms leading to ivabradine discontinuation=0;

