## 7. Summary of clinical events

### a) All-cause mortality

Death is obtained from the DEATH data

If DEATH.DTHDT is not missing then DEATH=1; else if participant is assessed at any time point, DEATH=0.

Restrict deaths to within 194 days of discharge. (non-missing DEATH.DTHDT – PATIENT.DISDT  $\leq$  194).

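### SAP Appendix 1 codes an event of interest or a death recorded without a usable date as no event

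*SAP*

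**What the plan says.** SAP Appendix 1, item 6, defines three participant-level tolerability variables, all built the same way.

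- Item 6(a), bradycardia, opens with "If EVENT.EVBRDC=1 and (non-missing EVENT.EVDT-PATIENT.DISDT", sets the limit at 194 days, and continues "then symptomatic bradycardia=1; else if participant is assessed at any time point, symptomatic bradycardia=0".
- Item 6(b), hypotension, opens with "If EVENT.EVHYPO=1 and (non-missing EVENT.EVDT-PATIENT.DISDT" and ends "then symptomatic hypotension=1; else if participant is assessed at any time point, symptomatic hypotension=0".
- Item 6(c), other symptoms, opens with "If AE.AETYP=3 and (non-missing AE.AESTDT-PATIENT.DISDT" and ends "Else if participant is assessed at any time point, other symptoms leading to ivabradine discontinuation=0".

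Item 7(a) has no separate flag for death: "If DEATH.DTHDT is not missing then DEATH=1; else if participant is assessed at any time point, DEATH=0". A further line restricts deaths to a non-missing difference between death and discharge dates of at most 194 days. Item 7(e) builds the composite from this variable and HF hospitalisation, giving 0 when both components are 0.

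The tolerability variables are compared between arms by Chi-square (SAP 9.3, item 3), as are the clinical events, including mortality and the composite (SAP 10). SAP 13.1 covers visit windows and last-contact dates for censoring. SAP 13.5 covers missing day-180 outcomes and imputation of heart rate, KCCQ and PGA. Neither gives a rule for a missing or partial event, death or discharge date.

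**The concern.** A missing date leaves the timing of an event unknown, but not whether it happened. These rules turn unknown timing into a recorded absence and keep the participant in the denominator. That differs from items 1(d), 5(b) and 5(c) of the same appendix, where a 0 requires the underlying value to be non-missing. The explicit non-missing condition suggests that the authors expected some dates to be absent.

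Undated events are plausible. Contacts are weeks to months apart, and at day 90 "participants should be contacted by the site (phone call) to assess for event status, current medication use and doses, and tolerability of ivabradine". SAP 13.1 also provides for vital status being established after loss to follow-up. Randomisation may precede the day of discharge (Protocol 4.2), so a participant could die before a discharge date exists.

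At stake are the named tolerability endpoints and the mortality table. Within an arm, the miscoding can only lower the count in these derived variables.

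**Working it through.** The plan states no figure on this point to reproduce. The check applies the rules literally to each combination of flag and dates.

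| Case (participant assessed at least once) | Result |
|---|---|
| Flag set, dated, at most 194 days after discharge | 1 |
| Flag set, event date missing | 0 |
| Flag set, discharge date missing | 0, if the non-missing condition applies to the whole difference |
| Flag set, dated after day 194 | 0 (intended) |
| Flag not set | 0 |
| Death dated, in window | 1 |
| Death known, death date missing | 0 |
| Death dated, discharge date missing | Set to 1, then fails the 194-day restriction; not countable, and the SAP does not say whether it becomes 0 or missing |

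A participant never assessed is left missing. Status is per participant, so a second, dated event of the same type still gives 1. An undated death makes the composite 0 unless the participant also has a counted HF hospitalisation.

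**Size per affected participant.** SAP 2.3 gives 104 enrolled and Protocol 6.2 gives 1:1 allocation. Assume 104 / 2 = 52 per arm. Then 1 / 52 = 1.9 percentage points.

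**Effect on a between-arm test.** The counts here are assumed, chosen near the 0.05 threshold. The test is Chi-square without continuity correction, N(ad − bc)² / [(a+b)(c+d)(a+c)(b+d)]. For 8 versus 2 of 52: 104 × (8×50 − 44×2)² / (52 × 52 × 10 × 94) = 104 × 312² / 2,541,760 = 3.98, p = 0.046.

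| Undated among the 8 | Table shows | Chi-square p |
|---|---|---|
| 0 | 15.4% v 3.8% | 0.046 |
| 1 | 13.5% v 3.8% | 0.081 |
| 2 | 11.5% v 3.8% | 0.141 |
| 3 | 9.6% v 3.8% | 0.240 |

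This shows only how sensitive the comparison is with arms this small. Fisher's exact test on 8 versus 2 already gives p = 0.092.

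**The case against.** The strongest reply is that missing dates should be rare and that the events are not lost from the report.

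- Protocol 12.6 requires an onset date in the source description of adverse events, Protocol 12.4 has monitors review events of interest, and Protocol 12.9 defines completion as all forms complete and all queries resolved. This makes undated events less likely, but it does not say what the analysis does when one remains.
- SAP 8.2 summarises adverse events by arm, including events of interest, at participant and event level with a listing and no stated date condition. An undated bradycardia should appear there. This stands: a reader might infer that undated events vanish from the safety reporting, and they do not. The consequence is that the SAP 8.2 table and the endpoint table could disagree.
- A reader might also infer that the loss falls more heavily on the ivabradine arm because its users are asked about tolerability. The documents do not support this. The Schedule of Assessments has events of interest assessed at every follow-up contact without regard to arm, the Executive Summary gives all participants the day-90 call, and usual-care participants may start ivabradine.
- It is tempting to say that in-hospital deaths are coded 0. The SAP does not say that the discharge date is blank in that case, or what an unevaluable difference becomes.
- These are tertiary endpoints and clinical-event tabulations. The primary analysis does not use these variables (SAP 9.1).

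Some pages, possibly including an earlier addendum, were not available, so a date convention there cannot be excluded.

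**Conclusion.** The point holds for missing event dates in items 6(a) to 6(c) and for missing death dates in item 7(a), with the composite in 7(e) following. The rules as written code a known event as its absence, and no other section supplied corrects this. For a dated death with a missing discharge date, the firm conclusion is narrower: it cannot be counted, and its final code is unspecified.

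The size is 1.9 percentage points of an arm's incidence per affected participant. This assumes 52 per arm and applies only to a participant with no other dated event of the same type. It is not the cost of every undated event. The number of affected participants is unknown and may be zero, so no overall bias can be stated and no difference between arms is shown. The correction is worth making because it is cheap and the arms are small.

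**What to change.** In SAP Appendix 1, items 6(a) to 6(c) and 7(a):

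1. Take status from the event flag or the death record, not from the presence of a date.
2. Code 0 only if no event is recorded or its date shows that it fell after day 194.
3. Count an event with a missing date as in-window if it was reported at or before the day-180 visit, or at the last study contact within day 194. List an undated event first reported later as undetermined. State how partial dates are handled.
4. Use the randomisation date as the anchor only if the discharge date is missing, and say how many participants this concerns.
5. Report the number of undated events by arm, and keep the current rule as a sensitivity analysis. Item 7(e) then follows.

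The cost is SAP wording and code. If there are no undated events or missing discharge dates, results do not change and the count shows it. An occasional undated event that fell after day 194 may be counted, because SAP 13.1 accepts visits up to 60 days outside their window. Using two anchors gives a few participants a slightly different window. Addendum 2 shows that SAP changes were still being decided after database lock and unblinding. If this change also comes after unblinding, it must be documented as such, in a supplement or an amendment as SAP 1 requires.

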### b) Symptomatic hypotension

Use the EVENT data to get unique participant level status.

If EVENT.EVHYPO=1 and (non-missing EVENT.EVDT-PATIENT.DISDT  $\leq$  194) then symptomatic hypotension=1; else if participant is assessed at any time point, symptomatic hypotension=0.

### c) Other symptoms leading to ivabradine discontinuation unique participant level status

Other symptoms leading to ivabradine discontinuation is obtained from the AE data.

If AE.AETYP=3 and (non-missing AE.AESTDT-PATIENT.DISDT  $\leq$  194) then other symptoms leading to ivabradine discontinuation=1;

Else if participant is assessed at any time point, other symptoms leading to ivabradine discontinuation=0;

## 7. Summary of clinical events

### a) All-cause mortality

Death is obtained from the DEATH data

If DEATH.DTHDT is not missing then DEATH=1; else if participant is assessed at any time point, DEATH=0.

Restrict deaths to within 194 days of discharge. (non-missing DEATH.DTHDT – PATIENT.DISDT  $\leq$  194).

### b) Worsening heart failure unique per participant

Worsening heart failure is defined as hospital admission for worsening signs and/or symptoms of HF or receiving unplanned intravenous (IV) diuretics for HF as an outpatient is obtained from hospitalization data (REHOSP) and ER/Clinic Visits (ERCLIN) data sets.

If REHOSP.RELHF=1 or ERCLIN.ERIVTMT=1 then Worsening heart failure =1; else if participant is assessed at any time point, worsening heart failure =0.

Restrict HF hospitalizations or ER visits for unplanned IV diuretics to within 194 days of discharge. (non-missing REHOSP.HOSPDT – PATIENT.DISDT  $\leq$  194) and (ERCLIN.ERVISDT- PATIENT.DISDT  $\leq$  194).

### c) HF hospitalization unique per participant

HF hospitalization is obtained from the hospitalization data (REHOSP),  
If REHOSP.RELHF=1 then heart failure hospitalization=1; else if participant is assessed  
at any time point, heart failure hospitalization=0.  
Restrict HF hospitalizations to within 194 days of discharge  
(non-missing REHOSP.HOSPDT – PATIENT.DISDT <= 194).

- d) All-cause hospitalization unique per participant  
All-cause hospitalization is obtained from the hospitalization data (REHOSP).  
If REHOSP.HOSPDT is not missing then all-cause hospitalization =1; else if participant  
is assessed at any time point, all-cause hospitalization=0.  
Restrict all-cause hospitalizations to within 194 days of discharge  
(non-missing REHOSP.HOSPDT – PATIENT.DISDT <= 194).
- e) Composite endpoint of mortality or HF hospitalization  
If DEATH (see ( a) above) =1 or HF hospitalization (see (c) above) =1 then  
Composite endpoint =1;  
Else if both are =0 then Composite endpoint=0.  
Event is restricted to within 194 days of discharge per component parts.

## **8) Barriers to acquisition of ivabradine**

Barriers to the acquisition of ivabradine comes from two sources. Barriers to the first  
time acquisition of ivabradine comes from the ivabradine obtaining first time data (EX).  
Get variables EX.EXPRC, EX.EXPHRM, EX.EXAE, EX.EXLBL, EX.EXPDC,  
EX.EXDDC, EX.EXPAN, EX.EXPAS, EX.EXINS, EX.EXAPN, EX.EXAPA,  
EX.EXAPD, and EX.EXOTH (Note: VISITID=60)

For subsequent visits, the data sources is the ivabradine usage (DRG) data (Note:  
VISITID=20, 30, 40, 50). Get variables  
DRG.DRPRC, DRG.DRPHRM, DRG.DRAE, DRG.DRLBL, DRG.DRPDC,  
DRG.DRDDC, DRG.DRPAN, DRG.DRPAS, DRG.DRINS, DRG.DRAPN,  
DRG.DRAPA, DRG.DRAPD, and DR.DROTH

Note: Since all reasons that apply are checked in both data sets, create separate (1/0)  
variables for each of them.

Summarize reasons from the (1/0) variables.

## **9) Treatment**

Treatment data come from the EDC system in the DAT\_RAND data. The data shows  
both the treatment codes and their descriptions.

## Appendix 2

### Mixed effects model analysis of repeated measures

Data were collected over time on continuous variables such as vital signs, labs and medication doses. Since within participant observations are likely to be correlated, using an analytic method that accounts for the correlation is appropriate. The mixed effects modeling approach provides a mechanism for accounting such correlations. Further, the procedure can include data from participants with partially complete data, and unequally spaced measurements which are evident in the data collected. Thus, for measurements that are collected over more than two time points, the mixed effects modeling approach is used. The model chosen includes treatment, time, and time by treatment interactions. Time will be modeled as a continuous variable which is the time to actual measurement expressed as days from randomization (DAYS). The model will assume a linear relationship between response measure and time, and allow for the intercept and slope of the linear model to differ by treatment group

The model posited is:

$$\text{Response (MEASURE)} = \text{intercept} + \text{Treatment (TRT)} + \text{Time (DAYS)} + \text{Treatment (TRT)*Time (DAYS)}$$

However, the test for treatment effect in the above model tests effects at baseline which is of little value.

It is more valuable to test treatment effects after the intervention had time to affect outcomes. Accordingly, the 180 day time point is recoded to time zero as follows.

$$\text{RDAYS} = \text{DAYS} - 180$$

And fit the model:

$$\text{Response (MEASURE)} = \text{intercept} + \text{Treatment (TRT)} + \text{Time (RDAYS)} + \text{Treatment (TRT)*Time (RDAYS)}$$

The within-patient residual covariance matrix will be modeled using a compound symmetry structure, which assumes equal correlation between measurement times within a patient. The residual covariance matrix will be assumed to be the same in the two treatment groups.

Tests of fixed effects in the model will be calculated using the Kenward-Roger method for estimating denominator degrees of freedom.

To fit the model the mixed effects model below is used;

```
proc mixed data=data;
Class TRT SUBNUM RDAYSC; *RDAYSC is defined to be equal to RDAYSC;
Model MEASURE= TRT RDAYSC TRT*RDAYSC / ddfm=KR;
Repeated RDAYSC /sub=SUBNUM TYPE=CS; /Compound symmetry covariance structure/
Run;
```

The test for treatment effect (TRT) in this model evaluates treatment effects at 180 days while the interaction term (TRT\*RDAYS) tests whether treatment effects differ over time, i.e., whether the slope (average change in measure per unit time) differs by treatment. The p-values for the treatment effect and treatment \* time interaction (when appropriate) will be reported.

If the equality of variance assumption does not hold (the variance differs a lot over time or across groups), the following code will be used. The model allows for unstructured covariance matrix.

```
proc mixed data=data method=reml;  
  class TRT VISIT SUBNUM;  
  Model Measure = TRT RDAY5 TRT*RDAYS/ solution ddfm=KR;  
  Repeated VISIT / subject=SUBNUM type=UN group=TRT;  
run;
```

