### **10.2 Sample Size Justification**

We assumed that 35% of participants randomized to the usual care arm will be treated with ivabradine at 180 days, and the pre-discharge initiation of ivabradine would increase the use at 180 days to 50%. The usual care event rate is based on investigator estimates of clinical use in the first year following approval by the Food and Drug Administration. At a two-sided Type I error rate of 0.05, 450 participants would provide 85% power to detect a significant difference in the rate of ivabradine use between groups. This sample size estimate is based on a two-group continuity corrected chi-square test and assumes a 1:1 allocation ratio between the pre-discharge initiation of ivabradine and usual care groups. This sample size estimate allows for 8% missing primary endpoint data.

For the KCCQ overall summary endpoint we have made a conservative assumption of 16 points for the standard deviation. For this measure, the medium and large clinically meaningful differences are 5 and 10 points for the KCCQ overall summary measure, respectively. Allowing for approximately 8% missing data, the proposed sample size of 450 participants provides approximately 90% power to detect a difference of 5 points

---

(medium clinically meaningful difference). The power calculations are based on the two sample t-test with a two-sided Type I error rate of 0.05.

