#### **5.2 Vital Signs and NYHA Class**

Participant vital signs will be summarized by randomization arm over time and analyzed with a mixed model approach, described in Appendix 2. Statistical test for the treatment and the

---

 Completers are participants who had an in-person day 180 visit.

treatment \* time interaction will be done. -The vital signs summarized include heart rate, systolic blood pressure, diastolic blood pressure and weight. NYHA class will be summarized by randomization arm in shift tables from baseline to worst post-baseline and baseline to 180 days. Improvement (worsening) will be evaluated using the Chi-Square test. Improvement is defined as moving from a higher NYHA class to a lower class from baseline. Worsening is defined as moving from a lower class to a higher class from baseline. A data listing of vital signs and NYHA class will be presented.

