### **5.4 Clinical Laboratory Results**

Descriptive summary of lab results of BNP and NT-proBNP will be presented by randomization arm over time. Moreover, summary change from baseline to 180 days will be presented by randomization arm. The data will be analyzed using the mixed model approach described in Appendix 2 after log transformation to correct the highly skewed nature of the data. A data listing of the lab measures BNP and NT-proBNP will be presented.

---

 The primary source of heart rate (at baseline and 180 days) is ECG assessment, if ECG assessment was not done at the 180 day visit, heart rate from vital signs assessment is used.

 BNP and NT-proBNP labs are deemed most relevant for this presentation.

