## **9.2 Secondary Analyses**

### **1. Heart Rate Assessments**

- a. Change in heart rate from baseline to 180 days will be compared across randomization groups. Change will be calculated as follows: (Baseline heart rate – 180 day heart rate). Comparisons across randomization groups will be performed using a linear model with adjustment for baseline heart rate and beta-blocker use. Randomization groups will be included in the regression model as main effect.

---

 Baseline beta-blocker use will be coded as a “0/1” variable with participants who received beta-blocker coded as “1” and those who did not receive beta-blocker as “0”.

 All change from baseline results presented are calculated similarly.

Heart rate is expected to be lower in the ivabradine arm than the usual care arm.  
Thus, change from baseline is expected to be higher in the ivabradine arm.

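### The Appendix 2 mixed model leaves the arms free to differ at baseline, so its day-180 contrast carries part of any chance imbalance and loses precision

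*SAP*

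**What the plan says.** Appendix 2 of the SAP regresses each measure on treatment, time in days from randomisation, and treatment by time. The model will "allow for the intercept and slope of the linear model to differ by treatment group". The SAP remarks that the treatment term, before any shift of the time axis, is a test at baseline. The baseline value is thus one of the responses. The SAP then subtracts 180 from time and states: "The test for treatment effect (TRT) in this model evaluates treatment effects at 180 days". Neither PROC MIXED block, main or fallback, has a baseline covariate or a common-baseline constraint.

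Three sections use this model:
- SAP 5.2: "Participant vital signs will be summarized by randomization arm over time and analyzed with a mixed model approach". The measures are heart rate, systolic and diastolic blood pressure, and weight.
- SAP 5.4, for BNP and NT-proBNP on the log scale: "The data will be analyzed using the mixed model approach described in Appendix 2".
- SAP 6, for dose data.

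SAP 9.2 takes a different line for the secondary heart-rate endpoint and uses a "linear model with adjustment for baseline heart rate and beta-blocker use". Its KCCQ and PGA models also adjust for the baseline value.

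**The concern.** Randomisation makes the expected baseline means equal, so a separate arm difference at day 0 is a parameter the trial does not need. Shifting the time origin moves the point at which treatment is tested, but leaves that difference free. If the arms happen to differ at baseline on a measure that tracks within person, part of the difference reappears as a treatment effect at day 180.

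Enrolment stopped at 104 of a planned 450, so sizeable chance imbalances are more likely than the design foresaw and precision is scarce. Heart rate would also receive two day-180 treatment tests, one adjusted for baseline and one not. The SAP does not say which governs if they disagree.

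**Working it through.** **The plan's own figure.** The documents give no precision or power figure for Appendix 2. The only related design figure is for the primary endpoint (Protocol 10.2): "At a two-sided Type I error rate of 0.05"; "We assumed that 35% of participants randomized to the usual care arm" would be on drug; and the intervention "would increase the use at 180 days to 50" per cent. A continuity-corrected chi-square test at 85% power needs 207 per arm, 414 in all. Then 414/0.92 = 450, and power with 414 evaluable is 85.1%. That figure reproduces, but it does not bear on this model.

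**Inputs.**
- Total enrolled: 104 (SAP 2.3). The split of 52 per arm is assumed.
- Compound symmetry and linear time: SAP Appendix 2.
- Measurement days 0, 12, 44 and 182 from randomisation: assumed from the visit schedule, with discharge about 2 days after randomisation.
- Complete data and outcome SD of 1: assumed.
- Within-person correlation r: not in the documents, so a range of 0.3 to 0.7 is shown.

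**Step 1: weights.** With complete data, the day-180 contrast is a weighted sum of the arm differences at the four visits. The weights are w_j = 1/4 + (180 − 59.5)(t_j − 59.5)/21043, where 59.5 is the mean time and 21043 the sum of squares about it. This gives −0.091, −0.022, 0.161 and 0.951. They sum to 1, and their squares sum to 1/4 + 120.5²/21043 = 0.940.

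**Step 2: SE as written.** Variance = (2/52)[r + 0.940(1 − r)].

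**Step 3: carry-over.** The expected shift in the day-180 effect per unit of observed baseline difference is r − 0.091(1 − r).

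**Step 4: rejection under no effect, given a 2-SE baseline imbalance.** The SE of a baseline difference is √(2/52) = 0.196 SD, so 2 SE is 0.392 SD. The contrast then has mean carry-over × 0.392 and variance SE² − carry-over² × 2/52. It is compared with ±1.96 SE.

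**Step 5: common baseline mean.** Baseline stays in the response with one mean. Treatment enters only as a post-baseline intercept and slope. Generalised least squares was solved numerically.

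| | r = 0.3 | r = 0.5 | r = 0.7 |
|---|---|---|---|
| SE as written (SD units) | 0.192 | 0.193 | 0.194 |
| Carry-over | 0.24 | 0.45 | 0.67 |
| Shift from a 2-SE imbalance (SD) | 0.09 | 0.18 | 0.26 |
| Rejection given that imbalance | 7% | 12% | 21% |
| SE with common baseline | 0.183 | 0.165 | 0.134 |
| Fall in variance | 9% | 27% | 52% |

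**Step 6: does it depend on linear time?** No. With visit as a category and a free baseline, the contrast has variance 2/52 and carry-over r. A common baseline mean multiplies the variance by 1 − r², a fall of 9%, 25% and 49%. The question is therefore separate from the first code block declaring time as a class variable while the text calls it continuous.

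**Step 7: a remedy to avoid.** A common intercept with a single slope difference forces the effect to grow linearly from zero at day 0. Its SEs look better (0.162 and 0.129 at r = 0.5 and 0.7). But if the true effect were constant after baseline, it would recover only 72% and 62% of that effect.

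**The case against.** The strongest reply is that a longitudinal model with a free baseline is valid and merely less efficient. That is right. Over repeated randomisations the contrast is unbiased within its linear model and type I error is 5%. A 2-SE imbalance arises by chance only about 5% of the time per measure.

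The analyses are also supportive. The primary endpoint uses logistic regression, the section 9.2 models adjust for baseline, and the tertiary beta-blocker dose comparison is a Wilcoxon test. SAP 13.6 calls everything outside the named endpoints exploratory, without p-values. That does not remove the point, because SAP 5.2 and Appendix 2 call for treatment tests and p-values from this model. That mismatch is a separate matter.

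The size depends on a correlation that nobody has stated. Eligibility truncates baseline heart rate at 70 bpm or more, which tends to lower its correlation with day 180. At r = 0.3 the gain is small. The complete-data assumption is also generous: the SAP expects more than 10% of day-180 heart rates to be missing, and the Protocol's schedule of assessments lists no BNP visits.

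The interaction test and the change-from-baseline summary in SAP 5.4 give partial cover. However, the interaction is a slope difference, not a day-180 effect. It is not immune to imbalance either, since its carry-over is −(1 − r)(59.5/21043) per day. Over 180 days at r = 0.5 that is −0.5 × 0.509 = −0.25.

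A reader might infer that the contrast is simply the raw arm difference at day 180. It is not. It is model-based and uses every visit, which is why the carry-over at r = 0.5 is 0.45 and not 0.50.

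**Conclusion.** The point holds as one of conditional bias and lost precision in supportive analyses, and the change should be made. As written, the day-180 contrast takes in about a quarter to two thirds of a chance baseline difference over r = 0.3 to 0.7. Its variance could be cut by about 9% to 52%. These figures rest on 52 per arm, complete data at the assumed days, compound symmetry, and an r that the documents do not supply.

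Two stronger readings are not supported. A reader might infer that the test has an inflated false-positive rate. The 7%, 12% and 21% figures apply only given a 2-SE imbalance, and the overall rate is 5%. A reader might also infer that the primary result or the secondary heart-rate, KCCQ and PGA results are affected. None of those uses Appendix 2. For heart rate, the two day-180 analyses can disagree, but only the section 9.2 analysis is the secondary endpoint.

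**What to change.** In both Appendix 2 code blocks, for vital signs, log BNP/NT-proBNP and beta-blocker dose:

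- Keep baseline in the response with one mean common to both arms.
- Allow treatment terms only after baseline: either an effect at each post-baseline visit, or a post-baseline intercept and slope. Do not force the effect to start at zero on day 0 and grow linearly.
- Report the day-180 contrast with its 95% CI.

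A baseline covariate with its interaction with time is a close alternative, but not an equivalent one, because it drops participants without a baseline value.

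Do not apply this to ivabradine dose. SAP Appendix 1 takes its baseline from in-hospital initiation, after randomisation, where the arms differ by design. For beta-blocker dose, confirm that the baseline-visit value was recorded before randomisation.

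State that the baseline-adjusted section 9.2 model governs day-180 heart rate.

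Addendum 2 shows that treatment has been unblinded. Make the change through the supplement or amendment route in SAP section 1, label it as post-unblinding, and show the planned model's results alongside.

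The cost is a few lines of SAP text and PROC MIXED code, with no new data.

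### SAP Appendix 2 keeps compound symmetry unless variances differ, so correlation that decays between visits goes unchecked and the linear-time treatment-by-time test can reject too often

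*SAP*

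**What the plan says.** SAP Appendix 2 sets one repeated-measures model for outcomes measured at more than two time points. SAP sections 5.2, 5.4 and 6 apply it to vital signs, BNP/NT-proBNP and medication doses. Time is continuous and linear, with an intercept and slope for each arm, and is re-centred so that the treatment term is the difference at day 180.

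- Default covariance: "The within-patient residual covariance matrix will be modeled using a compound symmetry structure, which assumes equal correlation between measurement times within a patient". The same matrix is assumed for both arms.
- Condition for switching to the unstructured code: "If the equality of variance assumption does not hold (the variance differs a lot over time or across groups". No numerical threshold is given, and unequal correlation is not mentioned.
- Interaction term: it "tests whether treatment effects differ over time", which the SAP explains as a difference in slope. P-values for treatment and for treatment-by-time are to be reported.
- Significance level: SAP 13.2 puts interaction tests generally at 0.10.
- Code: the compound-symmetry program puts its time variable in the CLASS statement, which makes time categorical. The fallback program has continuous time in the MODEL statement and adds `GROUP=TRT`, which gives each arm its own matrix.

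**The concern.** Compound symmetry makes two assumptions: equal variances over time and equal correlations between all pairs of visits. The SAP provides a check on the first only. Baseline and day 10 are likely to be more strongly correlated than baseline and day 180. If so, with equal variances, the check passes and compound symmetry stays.

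The slope contrast depends mainly on the long gap to day 180. Compound symmetry uses the average correlation over all pairs, which is too high for that gap, so the standard error of the slope difference comes out too small. Kenward-Roger does not repair this, because it works from the covariance model it is given. No robust variance is planned. At stake is whether a reported difference in trend for heart rate, blood pressure, weight, natriuretic peptide or dose is as certain as its p-value suggests.

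**Working it through.** **Stated figure.** The documents state no error rate or correlation for these models, so there is nothing to reproduce on this point.

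**Inputs from the documents.** 104 participants enrolled (SAP 2.3), taken as about 52 per arm under 1:1 allocation. Visits at baseline, day 7–14, day 42 and day 180 (SAP 13.1), entered as t = 0, 10, 42, 180. Medications are also recorded at the day-90 call (Protocol 5.5). Interaction level generally 0.10 (SAP 13.2).

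**Assumed.** Variance 1 at every visit, so the SAP's check passes. Correlation falls linearly with the gap: r(j,k) = a − (a − b)·|t_j − t_k|/180, written a→b. No true treatment effect.

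**Formulae.** Let x be the centred times, Sxx = Σx², R the correlation matrix and r̄ the mean off-diagonal correlation.

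- True variance of a participant's slope: x′Rx / Sxx²
- Variance under compound symmetry: (1 − r̄) / Sxx
- Ratio: V = x′Rx / [Sxx(1 − r̄)]
- Rejection rate at level α: 2[1 − Φ(z/√V)], with z = 1.96 (α = 0.05) or 1.645 (α = 0.10)

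**Worked case, 0.7→0.4.** Mean time is 58, so x = (−58, −48, −16, 122) and Sxx = 3,364 + 2,304 + 256 + 14,884 = 20,808. The six correlations are 0.683, 0.630, 0.400, 0.647, 0.417 and 0.470, so r̄ = 3.247/6 = 0.541. x′Rx = 14,399.7. V = 14,399.7 / (20,808 × 0.4589) = 1.508. The model's standard error is 1/√1.508 = 0.81 of the true one, about 19% too small. Rejection is 2[1 − Φ(1.96/1.228)] = 11.0% at 0.05 and 2[1 − Φ(1.645/1.228)] = 18.0% at 0.10.

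| Assumed correlation | V | Rejects at 0.05 | Rejects at 0.10 |
|---|---|---|---|
| Equal, 0.5 | 1.00 | 5.0% | 10.0% |
| 0.5→0.4 | 1.14 | 6.6% | 12.4% |
| 0.6→0.4 | 1.31 | 8.6% | 15.0% |
| 0.7→0.4 | 1.51 | 11.0% | 18.0% |
| 0.7→0.3 | 1.61 | 12.2% | 19.4% |
| 0.8→0.4 | 1.75 | 13.9% | 21.4% |
| Exponential decay, 0.7 at day 180 | 2.39 | 20.5% | 28.7% |

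Exponential decay with 0.1 to 0.7 remaining at day 180 gives 16.8–20.5% at 0.05. With five time points, as for doses, 0.7→0.4 gives 12.0% at 0.05.

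**Checks by simulation, 52 per arm.** Complete data, 20,000 runs: 4.8% at nominal 0.05 under true compound symmetry and 12.2% for 0.7→0.3. REML with 8–20% of visits assumed missing, 2,000 runs: 11.4% for 0.7→0.3.

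**Other tests from the same model, nominal 0.05.** The day-180 treatment test under linear time rejects about 5–6%. With time categorical by visit, the overall interaction F-test rejects about 5–8%.

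**With an unstructured covariance.** The exact growth-curve analogue (complete data, 10,000 runs) rejects 4.8–5.2% at nominal 0.05 in all four patterns tried: equal 0.5, 0.7→0.3, 0.8→0.4, and exponential decay with 0.3 remaining.

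**The case against.** The strongest reply is that no trial conclusion rests on these tests. The primary endpoint uses logistic regression (SAP 9.1). The secondary heart-rate, KCCQ and PGA changes use linear models at day 180 (SAP 9.2), and the tertiary dose comparisons use the Wilcoxon test (SAP 9.3). SAP 13.6 calls analyses outside the named endpoints exploratory and allows them no p-values, which conflicts with the p-values promised in section 5.2 and Appendix 2. All of this stands. It limits the importance of the point, but while the p-values remain planned, their error rate matters.

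The size is also open to challenge. A reader might infer that these p-values are known to be false-positive at 11–14% instead of 5%. The documents do not support that. They give no correlations, so any single range reflects an assumption. The SAP's general level for interactions is 0.10, not 0.05. The printed compound-symmetry code makes time categorical, where the overall interaction test is only mildly affected. The large inflation belongs to the linear-time slope test described in the text, so text and code must first be made to agree.

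Finally, the Appendix recodes time so that treatment is tested at day 180, and that test is close to nominal when variances are equal. This stands too.

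**Conclusion.** The gap is real: the default covariance assumes equal correlation across very unequal gaps, and the switching rule cannot detect a breach of that assumption when variances are equal. For correlations falling linearly from 0.5→0.4 up to 0.8→0.4, the linear-time treatment-by-time test rejects a true null about 12–21% of the time at the 0.10 level, or about 6.5–14% at 0.05. Pure exponential decay brings it to about 20% at 0.05. These figures rest on assumed correlations, equal variances, about 52 per arm, and the linear-time model in the text rather than the CLASS coding. For BNP and NT-proBNP the visit pattern is also assumed, since the protocol's schedule of assessments has no row for them.

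A reader might infer that the treatment p-values, or the secondary heart-rate result, are similarly compromised. They are not: the day-180 treatment test is little affected when variances are equal, and the secondary heart-rate endpoint uses a different model. The point deserves correction because the remedy is cheap, but its consequences are limited to supportive analyses.

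**What to change.** - Pre-specify for all Appendix 2 models an unstructured within-participant covariance by scheduled visit, common to both arms (`REPEATED VISIT / SUBJECT=SUBNUM TYPE=UN`, without `GROUP=TRT`), with Kenward-Roger.
- If it does not converge, use compound symmetry with empirical (sandwich) standard errors.
- Delete the trigger based on variance differing a lot over time. The same clause covers variance differing between arms. A common matrix drops that provision, in line with the Appendix's own assumption of one matrix for both arms. If the sponsor wants to keep it, name separate matrices as a sensitivity analysis.
- Make the time variable in the code continuous, to match the linear-time text, and keep a separate visit variable for the REPEATED statement.
- State the interaction level for these models, and reconcile section 13.6 with the p-values promised in section 5.2 and Appendix 2.

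The cost is SAP wording and an edit to the fallback code already printed. Four visits need 4 × 5 / 2 = 10 covariance parameters, and doses, with day 90 as a fifth time point, need 5 × 6 / 2 = 15. Both are feasible with 104 participants, at the price of slightly wider intervals.
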